7.3 TREATMENT PHASE

Weeks 4, 8, 12, and 24 assessments are listed below (in the recommended order):

- Vital signs (following at least 5 minutes of rest)
- WHO Functional Class for PAH
- AE assessment
- Drug accountability/compliance
- 12-lead ECG (Week 24 only; following at least 5 minutes rest in the semi-recumbent position)
- Concomitant medications
- 6MWT/Borg dyspnea score (6MWT to be initiated 3 to 6 hours after last dose of study drug and following at least 5 minutes of rest; Borg dyspnea score to be conducted immediately following 6MWT)
- Clinical worsening assessment
- Urine pregnancy test (for WOCBP)
- Clinical laboratory tests/NT-proBNP (Weeks 12 and 24 only)
- Continue administration of study drug and dose titration

- Continue at least weekly telephone contact (study drug dose at Weeks 16 and 20 must be recorded in the eCRF; at least monthly telephone contact initiated at Week 24)
- RHC (optional - Week 24 only; to be conducted within 72 hours following all other Week 24 assessments; as best as possible to be performed 3 to 6 hours after previous dose of study drug)

Continued Visits beyond Week 24 assessments include (in the recommended order):

- Vital signs (following at least 5 minutes of rest)
- WHO Functional Class for PAH
- AE assessment
- Drug accountability/compliance
- Concomitant medications
- 6MWT/Borg dyspnea score (6MWT to be initiated 3 to 6 hours after last dose of study drug and following at least 5 minutes of rest; Borg dyspnea score to be conducted immediately following 6MWT)
- Clinical worsening assessment
- Clinical laboratory tests/NT-proBNP (at the first Continued Visit and every other Continued Visit thereafter, e.g., Continued Visits #3, #5, #7, etc.)
- Urine pregnancy test (for WOCBP)
- Continue administration of study drug and dose titration
- Continue at least monthly telephone contact (study drug dose should be recorded in the eCRF on the day of Continued Visits (e.g. Weeks 36, 48, etc.) and every 30 days between Continued Visits)

Table 7-1 Continued Visits by Week Beyond Week 24

Continued Visit	Corresponding Study Week*
#1	36
#2	48
#3	60
#4	72
#5	84
#6	96
#7	108
#8	120
#9	132
#10	144
#11	156
#12	168
#13	180

Continued Visit	Corresponding Study Week*
#14	192
#15	204
#16	216
#17	228
#18	240

* Visit window is ± 14 days

Unscheduled Visits

Subjects may return to the study site at any time for additional assessments, including but not limited to clinical worsening, 6MWTs/Borg dyspnea score, AEs, or dispensing of additional study drug.

7.4 STUDY DRUG TERMINATION VISIT

Subjects will continue in the study until they experience clinical worsening, prematurely discontinue the study for any reason, or approximately 205 adjudicated clinical worsening events have occurred. If a subject remains ongoing with study treatment at the time when approximately 205 adjudicated clinical worsening events have occurred, the Study Drug Termination Visit should be scheduled as soon as possible. The following assessments will be conducted immediately after the decision is made to discontinue study drug (prior to down titration).

- Vital signs (following at least 5 minutes of rest)
- Physical examination
- Clinical worsening assessment
- WHO Functional Class for PAH
- AE assessment
- Drug accountability/compliance
- 12-lead ECG (following at least 5 minutes rest in the semi-recumbent position)
- Concomitant medications
- 6MWT/Borg dyspnea score (6MWT to be initiated 3 to 6 hours after last dose of study drug and following at least 5 minutes of rest; Borg dyspnea score to be conducted immediately following 6MWT)
- Urine pregnancy test (for WOCBP)
- Clinical laboratory tests/NT-proBNP

- Collection of blood sample for evaluation of blood biomarkers (optional)
- Collection of urine sample for evaluation of urine biomarkers (optional)
- Collection of blood sample for evaluation of pharmacogenomics (optional)

If the subject permanently discontinues study drug prior to Week 24 for any reason other than clinical worsening (e.g., AEs, addition of second PAH-approved oral therapy), the subject should immediately complete the study drug termination visit assessments and be encouraged to remain in the study and complete all visits up to and including Week 24. The Study Drug Termination Visit assessments should be conducted immediately after the decision is made to discontinue study drug (prior to down titration).

7.5 ACCESS TO THE OPEN-LABEL STUDY

Subjects who discontinue the study due to clinical worsening as reviewed by the Medical Monitor and undergo Study Drug Termination assessments will be eligible for the open-label extension study (TDE-PH-311) unless long-term (29 days or more) treatment with an infused or inhaled PGI₂ was initiated. Subjects who prematurely discontinue the study for any reason other than clinical worsening (e.g., AEs, withdrew consent, etc.) will not be eligible for entry into the open-label study.

Subjects who remain on study drug at the time that approximately 205 adjudicated clinical worsening events have occurred and complete Study Drug Termination assessments will be eligible for entry into the open-label extension study (TDE-PH-311) or may gain access to commercial drug if approved.

If a subject is eligible for the open-label extension study and received UT-15C during the blinded study then the subject may remain on the same dose of study drug upon entry into the open-label study. If the subject received placebo during the blinded study then the subject should start treatment with UT-15C in the open-label study in accordance with that protocol.

An IVRS/IWRS will be utilized to record appropriate efficacy data prior to providing each individual subject's treatment assignment to appropriate site personnel in order to start each subject on the appropriate dose of UT-15C in the open-label study.

See protocol TDE-PH-311 for more details regarding the open-label extension trial.

8 STUDY TERMINATION

8.1 CRITERIA FOR SUBJECT WITHDRAWAL

A subject may voluntarily withdraw or will be withdrawn from the study and/or study drug by the Investigator at any time for reasons including, but not limited to, the following:

- The subject wishes to withdraw from further participation
- A serious or life-threatening AE occurs or the Investigator considers that it is necessary to discontinue study drug to protect the safety of the subject
- The subject violated the protocol
- The subject's behavior is likely to undermine the validity of his/her results
- The subject experiences clinical worsening
- The subject becomes pregnant

If a subject is discontinued from the study prematurely, the Investigator will complete the End of Study Record for that subject and provide an explanation, if needed. For subjects who meet the definition of clinical worsening, the site must complete the specified eCRF page (see Section 3.2.1.1). If study drug has been administered, the Investigator should make every effort to perform all Study Drug Termination Visit assessments prior to study drug dose down-titration and study discontinuation.

8.2 CRITERIA FOR TERMINATING THE STUDY

The study may be stopped at any time if, in the opinion of the Investigator and/or sponsor, continuation of the study represents a serious medical risk to the subjects. This may include, but is not limited to, the presence of serious, life-threatening, or fatal AEs or AEs that are unacceptable in nature, severity, or frequency. The sponsor reserves the right to discontinue the study for any reason at any time.

The end of the study (study completion) will be declared and subjects will be transitioned out of the study based on the Data Monitoring Committee (DMC) and Sponsor's decision following the interim analysis, or approximately 205 adjudicated clinical worsening events have occurred, or the sponsor stops the study for any other reason.

8.3 CRITERIA FOR DISCONTINUING THE SITE

The study may also be terminated at a given center if:

- The Principal Investigator elects to discontinue the study
- The sponsor elects to discontinue the study at the site
- Applicable regulations are not observed
- The protocol is repeatedly violated or critical violations are documented
- Changes in personnel or facilities adversely affect performance of the study

9 ADVERSE EVENT REPORTING

9.1 DEFINITIONS

9.1.1 Adverse Event

An AE is any untoward medical experience occurring to a subject during a clinical trial whether or not it is related to the study drug. An AE may include an intercurrent illness, injury, or any other concomitant impairment of the subject's health, as well as abnormal laboratory findings if deemed to have clinical significance. AEs may also include worsening of an existing symptom or condition or pre/post-treatment events that occur as a result of protocol-mandated procedures.

9.1.2 Serious Adverse Event

An SAE is an AE occurring at any dose that results in any of the following outcomes:

- Death
- A life-threatening AE
- Inpatient hospitalization or prolongation of existing hospitalization
- A persistent or significant disability/incapacity
- A congenital anomaly/birth defect

In addition, important medical events that may not result in death, be life-threatening, or require hospitalization may be considered serious when, based upon appropriate medical judgment, they may jeopardize the subject and require medical/surgical intervention to prevent one of the outcomes listed above. Examples of such medical events include allergic bronchospasm requiring intensive treatment in an emergency room or at home, blood dyscrasias or convulsions that do not result in hospitalization, or the development of drug dependency or drug abuse.

Life-threatening means that the subject was, in the view of the Investigator, at immediate risk of death from the event as it occurred. It does not mean that the event, had it occurred in a more severe form, might have caused death.

Planned hospitalization for elective treatment or procedure for a pre-existing condition that did not worsen from the time of randomization (e.g. routine RHC) is not considered an SAE and does not meet the definition for clinical worsening.

9.1.3 Adverse Events Associated with Progression of PAH

Expected events that are related to the progression of a subject's PAH are defined in Appendix 15.6. All events that occur during the course of the study that are included on this list and felt to be related to the progression of the disease by the Investigator should not be recorded as AEs in the eCRF as these PAH symptoms will be evaluated and recorded as an efficacy endpoint and/or will be captured as disease related events.

However, an event must be recorded as an AE/SAE in the eCRF, if it meets one or more of the following criteria:

- There is a reasonable possibility that it may have been caused by study drug.
- It is serious.
- It has occurred at greater than expected severity (intensity, frequency, or duration).

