1.2.3 Clinical Pharmacology

In solution, both treprostinil sodium and treprostinil diethanolamine are disassociated from their respective salt counter-ions and exist as the freely ionized form of treprostinil. As a result, the bioactive form present in the bloodstream is identical irrespective of the selection of the counter-ion. Given this premise, the development of this new diethanolamine salt of treprostinil is expected to retain the bioactivity and safety profile of treprostinil sodium.

The most frequent adverse events (AE) associated with Remodulin in clinical trials of patients with PAH were related to the pharmacological properties of Remodulin and were generally not serious. These PGI₂-related AEs included diarrhea, headache, and nausea. Remodulin has not been associated with any significant changes in laboratory parameters or end-organ toxicity. The safety profile noted in the open label extension study, with much longer

durations of exposure and a larger, more diverse patient population, was consistent with the profile noted in the controlled trials. To date, well over 7000 subjects and patients have been exposed to Remodulin. This number includes patients who have received single administration, to patients receiving continuous infusion for greater than 10 years.

UT-15C has been administered to approximately 1800 subjects in Phase 1 to 3 clinical trials. UT-15C doses of up to 3 mg BID have been administered to healthy volunteers and patients with PAH have received up to 27.5 mg three times daily (TID) in the ongoing Phase 2 to 3 development program. The average exposure is approximately two years; the longest exposure is approximately seven years.

[figure not shown]

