3.2.2.4 Adverse Events

AEs will be captured from the time the ICF is signed. All AEs should be followed until either resolution (or return to normal or Baseline values), until they are judged by the Investigator to no longer be clinically significant, or for up to 30 days if the AE extends beyond the final visit. All SAEs should be followed until resolution, death, or the subject is lost to follow-up even if they are ongoing more than 30 days after completion of the final visit. Sections 9 and 15.4 provide the guidelines and definitions for recording AEs.

Symptoms of PAH (disease related events) should only be recorded as an AE if the event is either serious, new, or unusual with respect to intensity, frequency, duration as compared to symptoms in the subject's medical history; or there is a reasonable possibility that the event was caused by the study drug.

3.2.2.5 12-Lead ECG

Twelve-lead ECGs will be recorded after at least 5 minutes rest in the semi-recumbent position at Screening, Week 24, and at the Study Drug Termination Visit. Recordings should include lead II as a rhythm strip and contain at least five QRS complexes. ECG parameters collected include heart rate, PR interval, QT interval, QRS duration, and any clinically significant abnormalities.

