15.5 CHILD-PUGH SCORE

Parameter	Points		
	1	2	3
Hepatic encephalopathy	None (absent)	Stage I-II (mild or suppressed with medication)	Stage III-IV (severe or refractory)
Ascites	None (absent)	Mild-moderate (suppressed with medication)	Moderate-severe (refractory)
Bilirubin (total) $\mu\text{mol/L}$ (mg/dL)	<34 (<2)	34-50 (2-3)	>50 (>3)
Serum albumin (g/dL)	>3.5	2.8-3.5	<2.8
Prothrombin time (s)/INR	<4/(<1.7)	4-6/(1.71-2.20)	>6/(>2.20)

Class A (mild) = 5-6 points

Class B (moderate) = 7-9 points

Class C (severe) = 10-15 points (subjects in this class are excluded from participation)

15.6 EXPECTED EVENTS ATTRIBUTABLE TO THE PROGRESSION OF PULMONARY ARTERIAL HYPERTENSION (SYSTEM ORGAN CLASS AND PREFERRED TERM, VER. 16.0)

Abdominal pain (Gastrointestinal disorders; ABDOMINAL PAIN)	Hemoptysis (Respiratory, thoracic & mediastinal disorders; HAEMOPTYSIS)
Anorexia (Metabolism and nutrition disorders; ANOREXIA)	Hypoxia (Respiratory, thoracic & mediastinal disorders; HYPOXIA)
Ascites (Gastrointestinal disorders; ASCITES)	Loss of consciousness (Nervous system disorders; LOSS OF CONSCIOUSNESS)
Cardiac arrhythmia (Cardiac disorders; ARRHYTHMIA)	Nausea (Gastrointestinal disorders; NAUSEA)
Cardiac arrest (Cardiac disorders; CARDIAC ARREST)	Edema (General disorders and administration site conditions; OEDEMA)
Heart failure (including exacerbation of) (Cardiac disorders; CARDIAC FAILURE)	Orthopnea (Cardiac disorders; ORTHOPNOEA)
Chest pain (General disorders and administration site conditions; CHEST PAIN)	Pallor (Vascular disorders; PALLOR)
Cardiovascular collapse (Vascular disorders; CIRCULATORY COLLAPSE)	Palpitations (Cardiac disorders; PALPITATIONS)
Cor pulmonale (Cardiac disorders; COR PULMONALE)	Cool extremities (General disorders and administration site conditions; PERIPHERAL COLDNESS)
Cough (Respiratory, thoracic & mediastinal disorders; COUGH)	Pulmonary arterial hypertension, exacerbation of (Vascular disorders; PULMONARY ARTERIAL HYPERTENSION)
Cyanosis (Cardiac disorders; CYANOSIS)	Sudden death (Cardiac disorders; SUDDEN DEATH)
Dizziness (Cardiac disorders; DIZZINESS)	Syncope (Cardiac disorders; SYNCOPE)
Dyspnea at rest (Respiratory, thoracic & mediastinal disorders; DYSPNOEA)	Vasovagal reaction (Nervous system disorders; SYNCOPE VASOVAGAL)
Dyspnea on exertion (Respiratory, thoracic & mediastinal disorders; DYSPNOEA EXERTIONAL)	Tachycardia (Cardiac disorders; TACHYCARDIA)

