### **12.8 DISEASE-RELATED EVENTS**

All disease-related events occurring during the study will be listed for all subjects. Overall frequency of each type of event will be summarized by treatment group.

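### Protocol 3.2.2.4 and 9.1.3 give different rules for when a PAH symptom is recorded as an AE, so nausea counts can be split between the AE tables and the disease-related event table

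*Protocol*

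**What the plan says.** Protocol 3.2.2.4 states that symptoms of PAH "should only be recorded as an AE if the event is either serious, new, or unusual with respect to intensity, frequency, duration" relative to the subject's medical history, or if the study drug may reasonably have caused them. The section does not mention Appendix 15.6. It refers the reader to Sections 9 and 15.4 for AE recording guidance.

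Protocol 9.1.3 covers events on the Appendix 15.6 list that the investigator considers due to progression. These "should not be recorded as AEs in the eCRF as these PAH symptoms will be evaluated and recorded as an efficacy endpoint". The same sentence then names a second destination for them: "and/or will be captured as disease related events". Three conditions override this and require an AE record: "There is a reasonable possibility that it may have been caused by study drug"; the event is serious; or "It has occurred at greater than expected severity (intensity, frequency, or duration").

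Appendix 15.6 includes "Nausea (Gastrointestinal disorders; NAUSEA"). Protocol 1.2.3 says of the injected form of treprostinil that its prostacyclin-related "AEs included diarrhea, headache, and nausea". Protocol 1.2.4 names nausea again among the expected AEs in the oral trial TDE-PH-302.

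SAP 12.2 restricts the AE summary tables to treatment-emergent AEs and adds AE rates per patient-year because exposure may differ between arms. SAP 12.8 handles disease-related events separately: they are listed, and "Overall frequency of each type of event will be summarized by treatment group" (Table 14.3.7, Listing 16.2.6.12). No output combines the two sources.

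**The concern.** Two sites that both follow the protocol can record the same event differently, depending on which section they read. For a term that is both a listed progression event and a known drug effect, the number in the AE table then depends partly on that choice and partly on the investigator's blinded view of cause. An event that goes to the disease-related form is absent from the AE incidence tables, the patient-year rates, and the tables by intensity, causality and dose at onset.

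This bears on a question the trial itself raises. Protocol 1.4 gives fewer prostacyclin-type AEs as one of the hoped-for benefits of the change from BID to TID dosing. A nausea count that can be divided between two tables is a weak basis for judging that.

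**Working it through.** No sample size, alpha or event count is involved, so the check compares the two sets of criteria and follows each recording route to its output.

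**Step 1: criteria side by side**

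| Criterion that makes the event an AE | Protocol 3.2.2.4 | Protocol 9.1.3 |
|---|---|---|
| Serious | Yes | Yes |
| Drug cause reasonably possible | Yes | Yes |
| New | Yes | Not mentioned |
| Unusual or greater severity | Yes, against the subject's medical history | Yes, against an undefined expectation |

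The sections agree on two criteria and differ on two.

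**Step 2: do they cover the same events?** Section 3.2.2.4 speaks of PAH symptoms in general, and 9.1.3 of listed events attributed to progression. Section 9.1.3 itself calls the latter PAH symptoms, so they fall within the scope of 3.2.2.4. The rules overlap and cannot be read as covering separate sets.

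**Step 3: test case.** Take a subject with no nausea in the history who has a first episode. It is non-serious and of ordinary severity. The investigator attributes it to progression and judges drug cause not reasonably possible.
- Under 3.2.2.4 it is new, so it is an AE.
- Under 9.1.3 it is listed, attributed to progression and meets none of the three overrides. It is not an AE and goes to disease-related events.

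**Step 4: overlap with drug effects.** The effects that the protocol names from clinical studies in 1.2.3 and 1.2.4 are headache, diarrhea, nausea, flushing and jaw pain. Only nausea is in Appendix 15.6. Vomiting is listed too, but is named as a drug finding only in dogs (1.2.2).

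**Step 5: where the counts go.** The AE route leads to the SAP 12.2 tables and patient-year rates. The disease-related route leads to Table 14.3.7, for which SAP 12.8 plans an overall frequency by arm and no patient-year rate.

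**Step 6: can the effect on the comparison be signed?** Suppose that the proportions with nausea are p1 (active) and p0 (placebo), that fractions d1 and d0 of these subjects have their nausea recorded only as disease-related, and that each subject falls wholly in one table. The AE table then shows p1(1 − d1) and p0(1 − d0).
- If d1 = d0 = d, the risk ratio is p1(1 − d) / [p0(1 − d)] = p1/p0, which is unchanged. The absolute difference becomes (p1 − p0)(1 − d), which is smaller.
- If d1 and d0 differ, the risk ratio is multiplied by (1 − d1)/(1 − d0), which can be above or below 1.

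The documents give none of these four quantities for this trial, so neither size nor direction follows.

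**The case against.** The case for leaving the text alone has several parts.

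- **Nothing is lost.** Events kept off the AE page are still captured, listed and summarised by arm. This stands. A reader might infer that such events disappear from the safety data, and the documents do not support that. They can leave only the AE tables.
- **Section 3.2.2.4 points to Section 9.** That shows where the detailed guidance is, but 3.2.2.4 still states its own rule, and the two rules differ. One could also read a symptom absent from the history as exceeding expected frequency, which would bring it back as an AE under 9.1.3. With the expectation undefined, that reading is possible but not secured.
- **Both sections protect suspected drug effects.** This stands in large part. Nausea is a recognised class effect, and at least weekly calls during the first 24 weeks (Protocol 6.1) monitor AEs and guide titration, so a blinded investigator would often consider drug cause possible. The safeguard is partial because it rests on that judgement. The causality definitions in Protocol 15.4 also allow an event to be called not related when concurrent disease is a reasonable cause, and every subject has PAH. Those definitions grade causality, however, and do not replace the recording threshold in 9.1.3.
- **The divergent case is narrow.** This stands. The clearest case needs all the conditions in Step 3 together.

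Two stronger readings are tempting. One is that the AE tables under-count more in the active arm and so understate harm. Drug-induced nausea linked in time to dosing is what the causality override should catch, so diversion could equally be lower in that arm. The other is that the whole list masks drug effects. Abdominal pain and dizziness are listed, but the protocol does not name them as clinical effects of the drug.

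**Conclusion.** The criteria mismatch is wrong as written. The treatment of a new symptom and the severity comparator both differ between 3.2.2.4 and 9.1.3, and at least one plausible event is classified in opposite ways. The practical consequence is limited to possible splitting of counts for overlapping terms, with nausea the one firm example. Serious events are AEs under both rules, and the primary endpoint definition is not affected.

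The severity is minor. The conclusion assumes only that some investigators attribute a first nausea to progression and judge drug cause not reasonably possible. How often that happens, and whether it differs by arm, cannot be determined from the documents. No figure for an under-count is justified.

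**What to change.** **Protocol.** Reconcile 3.2.2.4 and 9.1.3 to one set of criteria. State whether a new symptom counts as an AE, and against which comparator severity is judged. The cost is a wording correction.

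**SAP 12.2/12.8.** Add one supportive table by arm that pools AEs and disease-related events for Appendix 15.6 terms, at least nausea. Show the number and percentage of subjects, counting each subject once per term. Add patient-year rates only if the disease-related form records individual events; the documents do not describe that form. This table does not depend on which recording rule a site followed or on the blinded attribution of cause, so it remains useful for data already collected.

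The pooled table is a cheap improvement rather than a correction. Its drawback is that it also contains true disease symptoms, so it should sit beside the planned AE tables and not replace them. The endpoint, alpha and sample size are unchanged.
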